7.1.3 Guidelines for Evaluation of Measurable Disease

All measurements should be recorded in metric notation, using calipers if clinically assessed. All baseline evaluations should be performed as close as possible to the treatment start and never more than 4 weeks before the beginning of the treatment.

The same method of assessment and the same technique should be used to characterize each identified and reported lesion at baseline and during follow-up. Imaging based evaluation should always be done rather than clinical examination unless the lesion(s) being followed cannot be imaged but are assessable by clinical exam.

Clinical lesions: Clinical lesions will only be considered measurable when they are superficial and > 10 mm diameter as assessed using calipers (e.g. skin nodules). For the case of skin lesions, documentation by color photography including a ruler to estimate the size of the lesion is suggested. As noted above, when lesions can be evaluated by both clinical exam and imaging, imaging evaluation should be undertaken since it is more objective and may also be reviewed at the end of the study.

Chest X-ray: Chest CT is preferred over chest X-ray, particularly when progression is an important endpoint, since CT is more sensitive than X-ray, particularly in identifying new lesions. However, lesions on chest X-ray may be considered measurable if they are clearly defined and surrounded by aerated lung.

CT, MRI: CT is the best currently available and reproducible method to measure lesions selected for response assessment. This guideline has defined measurability of lesions on CT scan based on the assumption that CT slice thickness is 5mm or less. When CT scans have slice thickness greater than 5 mm, the minimum size for a measurable lesion should be twice the slice thickness. MRI is also acceptable in certain situations (e.g. for body scans).

Ultrasound: Ultrasound is not useful in assessment of lesion size and should not be used as a method of measurement. Ultrasound examinations cannot be reproduced in their entirety for independent review at a later date and, because they are operator dependent, it cannot be guaranteed that the same technique and measurements will be taken from one assessment to the next. If new lesions are identified by ultrasound in the course of the study,

confirmation by CT or MRI is advised. If there is concern about radiation exposure at CT, MRI may be used instead of CT in selected instances.

Endoscopy, laparoscopy: The utilization of these techniques for objective tumor evaluation is not advised. However, they can be useful to confirm complete pathological response when biopsies are obtained or to determine relapse in trials where recurrence following complete response or surgical resection is an endpoint.

Tumor markers: Tumor markers alone cannot be used to assess objective tumor response.

7.1.4 Response Criteria

7.1.4.1 Evaluation of Target Lesions

Patients will be evaluated according the following RECISTv1.1 response:

Complete Response (CR): Disappearance of all target lesions, determined by two separate observations conducted not less than 4 weeks apart. There can be no appearance of new lesions.

Partial Response (PR): At least a 30% decrease in the sum of the longest diameter (LD) of target lesions, taking as reference the baseline sum LD. There can be no appearance of new lesions.

Progressive Disease (PD): At least a 20% increase in the sum of the LD of target lesions (with a minimum absolute increase of 5 mm), taking as reference the smallest sum LD recorded since the treatment started, or the appearance of one or more new lesions.

Stable Disease (SD): Neither sufficient shrinkage to qualify for PR (taking as reference the baseline sum LD) nor sufficient increase to qualify for PD (taking as reference the smallest sum LD since the treatment started).

For Cohort B only:

After the first PD assessment per RECISTv1.1 (=irSD per irRECIST), patients will be evaluated for irPD at least 4 weeks apart according to the following definition:

Immune-related Progressive Disease (irPD): At least a 20% increase in the sum of the LD of target lesions (with a minimum absolute increase of 5 mm), taking as reference the smallest sum LD recorded since the treatment started, or appearance of new lesions since the last evaluation.

7.1.4.2 Evaluation of Non-Target Lesions

Complete Response (CR): Disappearance of all non-target lesions. All lymph nodes should be non-pathological in size (<10 mm short axis)

Non-CR/Non-OD: Persistence of one or more non-target lesion(s).

Progressive Disease (PD): Appearance of one or more new lesions and/or unequivocal progression of existing non-target lesions.

Although a clear progression on non-target lesions in absence of stable target lesions is exceptional, the opinion of the treating physician should prevail in such circumstances.

7.1.4.3 Evaluation of Best Overall Response

The best overall response is the best response recorded from the start of the treatment until disease progression/recurrence (taking as reference for progressive disease the smallest measurements recorded since the treatment started). The patient's best response assignment will depend on the achievement of both measurement and confirmation criteria.

Evaluation as per combined RECISTv1.1/irRECIST

Target Lesions	Non-Target Lesions	New Lesions	Overall Response per RECISTv1.1	Overall Response per irRECIST (Cohort B only)	Confirmed Response for this Category Requires:
CR	CR	No	CR	NA	>4 wks. confirmation
CR	CR Non-CR/PD	No	PR	NA	>4 wks. confirmation
PR	CR Non-CR/PD	No			
SD	CR Non-CR/PD	No	SD	NA	Documented at least once \geq 4 wks. from baseline
PD	Any	Any	PD	irSD	>4 wks. confirmation
Any	PD*	Any			
Any	Any	Yes			
PD	Any	Any	NA	irPD	No further confirmation required
Any	PD*	Any			
Any	Any	Yes			

* Only in exceptional circumstances, unequivocal progression in non-target lesions may be accepted as disease progression.

Note: Patients with a global deterioration of health status requiring discontinuation of treatment without objective evidence of disease progression at that time should be reported as "*symptomatic deterioration*". Every effort should be made to document the objective progression even after discontinuation of treatment.

NA=not applicable

Note: If subjects respond to treatment and are able to have their disease resected, the patient's response will be assessed prior to the surgery.

7.1.4.4 Treatment Beyond Progression – Cohort B only

Accumulating evidence indicates a minority of subjects treated with immunotherapy may derive clinical benefit despite initial evidence of PD.

Subjects treated on Arm B will be permitted to continue study treatment beyond initial RECISTv1.1 defined PD, assessed by the investigator, as long as they meet the following criteria:

- Investigator determined clinical benefit
- Tolerance of study drug
- Stable performance status

- Treatment beyond progression will not delay an imminent intervention to prevent serious complications of disease progression (e.g., CNS metastases)

A radiographic assessment/ scan should be performed within 4-8 weeks of initial investigator-assessed progression to determine whether there has been a decrease in the tumor size or continued PD (termed irPD). The assessment of clinical benefit should be balanced by clinical judgment as to whether the subject is clinically deteriorating and unlikely to receive any benefit from continued treatment.

If the investigator feels that the subject continues to achieve clinical benefit by continuing treatment, the subject should remain on the trial and continue to receive monitoring according to the Time and Events Table (Section 6.1).

Immune-related Progressive Disease (irPD): For the subjects who continue study therapy beyond progression, further progression is defined as an additional 10% increase in tumor burden with a minimum 5 mm absolute increase from time of initial PD, unequivocal worsening of NT lesions, or appearance of new lesions since the last evaluation. This includes an increase in the sum of diameters of all target lesions and/ or the diameters of new measurable lesions compared to the time of initial PD. Study treatment should be discontinued permanently upon documentation of further progression (i.e. irPD).

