6.0 SCHEDULE OF ASSESSMENTS

6.1 Time and Events Table

1 cycle (C) = 28 days (D).

Trial Period	Screening (-28 to -1 days)	C1D1	C2D1	C3D1	C4D1	Additional Cycles...	EOT ⁷	Follow-Up ⁸
							30 days from last dose (+/- 7 business days)	Every 12 weeks (+/-14 business days) for up to 24 months/death
Informed Consent	X							
Tumor tissue specimen (15 FFPE slides required; blocks preferred) identified	X							
Blood for banking		X						
History, PE, Concomitant Meds, Vital Signs ¹	X	X	X	X	X	X	X	
PT/INR, aPTT	X							
Karnofsky Performance Status	X	X	X	X	X	X	X	
Pregnancy Test for WOCBP ²	X							
Toxicity (include DLT) Evaluations ¹²	X	X	X	X	X	X	X	
CBC with differential, platelets ³	X	X ¹³	X ¹³	X	X	X	X	
COMP ⁴	X	X	X	X	X	X	X	
TSH	X	Every 12 weeks from Cycle 1 Day 1 ⁵						
QoL (EQ-5D-5L)		X	X	X		X ¹⁴		X
Pill Diary collection/handing out		X	X	X	X	X		
Tumor response assessment ⁶ (CT chest, CT or MRI abdomen/pelvis; CT or MRI brain if clinically indicated)	X			X		X ⁶		X
Treatment								
ESK98 ^{9, 10} (Cohort A and B)		X	X	X	X	X		
Nivolumab ¹¹ (Cohort B only)		X	X	X	X	X		
Survival Status								X

1. Vital signs will include weight, temperature, pulse, respirations, blood pressure; height will be obtained at screening only.
2. WOCBP: Women of child bearing potential; either urine or serum pregnancy test.
3. CBC with diff includes total WBC, hemoglobin, hematocrit and differential of the WBC including absolute counts. Other checks are at discretion of treating investigator.

4. COMP or Comprehensive metabolic profile includes sodium, potassium, chloride, bicarbonate, BUN, creatinine, AST, ALT, alkaline phosphatase, total bilirubin.
5. TSH: Every 12 weeks from Cycle 1 Day 1 (i.e. Cycle 4 Day 1; Cycle 7 Day 1, etc.).
6. Window of +/- 7 business days. Imaging will be with or without intravenous contrast, before or on associated visit. CT or MRI brain with (preferred) or without IV contrast if suspected or known brain metastases. Frequency of tumor assessments will be q2 cycles (i.e. q 8 weeks) for first 4 assessments beyond baseline and then q 3 cycles (i.e. 12 weeks) subsequently until withdrawal of consent/death/2 years from C1 D1 whichever is later. If CR/PD, should be confirmed with repeat imaging after an interval of at least 4 weeks. In follow-up, if subjects are on alternative therapies, no mandated imaging but data from routine imaging will be captured at least every 12 weeks if available (+/- 7 business days).

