7.0 MEASUREMENT OF EFFECT

7.1 Antitumor Effect- Solid Tumors

Immunotherapy drugs such as nivolumab can initially cause inflammation in the early stages of treatment. Immune-related RECIST (irRECIST) utilizes RECISTv1.1 but considers an inflammatory response (or "pseudo-progression") as normal. The main difference between RECISTv1.1 and irRECIST is that patients can stay on trial after the first progressive disease (PD) assessment (as per RECISTv1.1) if using immune-related RECIST criteria. This PD per RECISTv1.1 is then re-labeled as immune related stable disease (irSD) per irRECIST and requires addition of unidimensional measurements of all new lesions (that meet the definition of target lesion) to be added to the sum of longest diameters (SLD) calculation for response assessment. Importantly, immune-related progression (irPD) must be confirmed by a follow-up scan at least 4 weeks (within 4-8 weeks) following the initial PD/irSD assessment in order to take the patient off the trial.

Subjects that are deemed to have clinical progression and/or unstable should not be continued on therapy after PD (per RECISTv1.1) and are therefore not required to have repeat tumor imaging for confirmation as per irPD definition. It is at the discretion of the treating investigator whether to continue a subject on study treatment until repeat confirmatory imaging is obtained. This clinical judgment decision by the site investigator should be based on the subject's overall clinical condition, including performance status, clinical symptoms, and laboratory data.

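### In Cohort B, irPD has two target-lesion rules, and patients excused from the confirming scan have no stated irRECIST PFS event date

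*Combined protocol and SAP*

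**What the plan says.** Section 2.5.3 lists irRECIST PFS and response by combined RECIST 1.1 and irRECIST as secondary endpoints for Cohort B.

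The definitions come from several places:

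- **Section 7.1.4.1**, Cohort B, after first PD: "Immune-related Progressive Disease (irPD): At least a 20% increase in the sum of the LD of target lesions", with a 5 mm minimum, measured against the smallest sum since treatment start; new lesions also count.
- **Section 7.1.4.4**: "further progression is defined as an additional 10% increase in tumor burden with a minimum 5 mm absolute increase from time of initial PD"; unequivocal non-target worsening or new lesions also count. This section asks for a scan 4-8 weeks after initial PD "to determine whether there has been a decrease in the tumor size or continued PD (termed irPD", and adds: "Study treatment should be discontinued permanently upon documentation of further progression (i.e. irPD".
- **Section 7.1**: "This PD per RECISTv1.1 is then re-labeled as immune related stable disease (irSD) per irRECIST". irPD then needs a confirming scan, but patients with clinical progression or an unstable condition "are therefore not required to have repeat tumor imaging for confirmation as per irPD definition".
- **Section 6.1, footnote 6**: tumor assessments run "until withdrawal of consent/death/2 years from C1 D1 whichever is later". PD should be confirmed by repeat imaging. Imaging is not mandated once a patient is on another therapy, although routine scans are captured.
- **Section 7.1.6** defines PFS only as time to progression or death. **Section 11.4** does not mention irRECIST.
- **The table in Section 7.1.4.3** shows only NA, irSD or irPD in its irRECIST column. Section 7.1.2 says that response is recalculated with new lesions added to the sum.

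**The concern.** One term carries two thresholds and two reference points. Both apply to Cohort B patients rescanned after a first RECIST 1.1 PD, and no sentence gives either one priority. Section 7.1.4.4 makes irPD the trigger for permanent discontinuation, so the same scans could stop or continue treatment depending on which section is read. A sum that has stopped growing after apparent pseudo-progression is the case that treatment beyond progression is meant to accommodate, and it is the case on which the two rules differ.

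The PFS gap is a separate matter. A patient who stops for clinical deterioration without the rescan has irSD as the last irRECIST category. The event could then be dated at first PD, at a later routine scan or at death, or the patient could be censored. Without a written rule the choice can be made after the data are seen. Any date later than first PD lengthens irRECIST PFS in the patients who are doing worst.

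Finally, a response that follows initial PD has no row in the table. As tabulated, the combined response rate cannot exceed the RECIST 1.1 rate.

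**Working it through.** The plan gives no figure for irRECIST PFS, so there is none to reproduce. The lesion sums below are illustrative.

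**1. The two target-lesion rules.** Let N be the nadir sum, P the sum at first PD and S the sum at rescan, in mm.

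- Rule A (7.1.4.1): S ≥ max(1.2N, N+5).
- Rule B (7.1.4.4): S ≥ max(1.1P, P+5).

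If first PD was target-driven, then P ≥ max(1.2N, N+5). An unchanged sum (S = P) therefore always meets A and never meets B.

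| N | P | A met from | B met from | S where only A is met |
|---|---|---|---|---|
| 50 | 62 | 60.0 | 68.2 | 60.0-68.1 |
| 80 | 100 | 96.0 | 110.0 | 96.0-109.9 |
| 100 | 125 | 120.0 | 137.5 | 120.0-137.4 |

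A shrinking sum can also fall in the gap. With 80/100/97, 97/80 = 1.2125 (+21%, +17 mm), so A is met; 97/100 = 0.97 (-3%), so B is not.

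**2. The reverse direction.** Suppose first PD came from non-target progression and the target sum was still at nadir (P = N). Then B is met before A: from 55.0 against 60.0 mm at N = 50, and from 110.0 against 120.0 mm at N = 100. With a stable measurable new lesion of size L, P = N + L, and B comes first when 1.1(N+L) < 1.2N, that is, L < N/11. At the 10 mm non-nodal minimum N must exceed 110 mm; at the 15 mm nodal minimum, 165 mm.

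The 7.1.4.3 table limits this. Its irPD rows include non-target PD with any target status, and any new lesion. Section 7.1.4.2 defines non-target PD as "Appearance of one or more new lesions and/or unequivocal progression of existing non-target lesions". While that finding is still scored at the rescan, the table gives irPD whatever the target sum. The B-only bands therefore apply only if the earlier non-target PD or new lesion is no longer scored as such.

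**3. Effect of event dating on irRECIST PFS.** The inputs are assumptions; the documents give none of them.

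- Time to first PD: exponential, median 6 months.
- Share of patients unscanned: 10%, 20% or 40%.
- Delay from first PD to death in those patients: exponential, median 3 or 6 months.
- The delay is either cut at 84 days (2.76 months), as if a follow-up scan recorded irPD by then, or left uncut, as if no later scan were ever captured.

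Medians from 4,000,000 simulated patients, against 6.0 months when every event is dated at first PD:

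| Unscanned share | Cut at 84 days (3 / 6 month delay) | Uncut (3 / 6 month delay) |
|---|---|---|
| 10% | 6.23 / 6.27 | 6.44 / 6.64 |
| 20% | 6.46 / 6.53 | 6.90 / 7.36 |
| 40% | 6.90 / 7.04 | 7.85 / 9.01 |

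For scale, with 36 events an exponential 95% CI for a 6-month median is 6 × exp(±1.96/√36) = 4.33 to 8.32. Only the 9.01 figure lies outside it.

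The plan is also silent on whether a scan-confirmed irPD is dated at first PD or at the confirming scan. The difference is 28 to 56 days, or 0.92 to 1.84 months, for each such patient.

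**4. Response table.** One response after initial PD among 36 patients is 1/36 = 2.8 percentage points.

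**The case against.** The strongest defence is a sequential reading: the nadir rule decides the 4-8 week scan, and the 10% rule applies afterwards to those who continue. This fits the order of Section 7.1.4.4, which introduces the 10% rule for subjects already continuing beyond progression. An unchanged sum still 20% above nadir could also be called continued PD at the 4-8 week scan. This reading is possible but nowhere stated. The 10% rule is measured from initial PD and is not restricted to later scans. What the objection does establish is that an unchanged sum fails the 10% rule; it does not establish that Section 7.1.4.4 as a whole excludes irPD.

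A reader might infer that the two rules conflict equally in both directions. The table in 7.1.4.3 does not support that, as shown above, and it accepts non-target progression only exceptionally.

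The consequence for treatment is also softened. The explicit instruction to stop sits beside the 10% rule only. Section 7.1.4.1 contains none, although Section 5.6 refers generally to progression as defined in Section 7.0. The investigator has discretion to continue until the confirming scan.

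On PFS, a reader might infer a serious inflation from the 9.0-month figure. That needs 40% of patients unscanned and no later scan ever captured, whereas footnote 6 continues assessments and collects routine imaging. The endpoint is descriptive, single-arm and has no threshold. These points limit the size of the problem; they do not supply the missing date.

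**Conclusion.** The point holds as an inconsistency that should be corrected before analysis. After a target-driven first PD, an unchanged or slightly shrinking sum is irPD under 7.1.4.1 and does not meet the 10% rule of 7.1.4.4; this is arithmetic and needs no assumption beyond the illustrative sums. The reverse disagreement is confined to cases where the earlier non-target PD or new lesion is no longer scored.

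Read literally, patients excused from the confirming scan have no irRECIST progression date. The direction of the effect is clear: later dating lengthens irRECIST PFS. Its size rests wholly on the assumed median, delay and unscanned share, and most of the computed shifts are smaller than the sampling uncertainty. The gap in the response table is minor.

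The reach is Cohort B stopping decisions and the descriptive secondary irRECIST endpoints. A reader might carry the concern over to the main efficacy conclusion, but the primary ORR uses RECIST 1.1, and neither it, the Simon decisions, RECIST PFS nor OS depends on irPD.

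**What to change.** - **One irPD rule in both sections.** A workable choice is the 7.1.4.4 rule: an additional 10% and at least 5 mm from initial PD with new measurable lesions included, or unequivocal non-target worsening, or further new lesions. Align 7.1.4.1 and the irPD rows of the 7.1.4.3 table with it.
- **An irRECIST PFS rule in 11.4.** Date the event at first RECIST 1.1 PD in two situations: when the confirming scan shows irPD, and when the patient stops for clinical progression without the 4-8 week scan. In the second situation, do so regardless of any later routine scan. Report how many patients were unconfirmed. Censor patients without an event at the last evaluable scan.
- **irCR and irPR rows after initial PD** in the 7.1.4.3 table, consistent with the recalculation in 7.1.2.

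The cost is wording only, with no extra scans or patients. irRECIST PFS may come out slightly shorter than under later dating.

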7.1.5 Duration of Response

Duration of overall response: The duration of overall response is measured from the time measurement criteria are met for CR or PR (whichever is first recorded) until the first date that recurrent or progressive disease is objectively documented (taking as reference for progressive disease the smallest measurements recorded since the treatment started).

Duration of stable disease: Stable disease is measured from the start of the treatment until the criteria for progression are met, taking as reference the smallest measurements recorded since the treatment started.

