2.5 Secondary Endpoints

2.5.1 To assess the objective response rate (complete response and partial response) by RECIST 1.1 in metastatic renal cell cancer to ESK981 monotherapy.

2.5.2 To determine frequency and severity of adverse events by CTCAE criteria of ESK981 in patients with metastatic renal cell carcinoma.

2.5.3 To evaluate secondary efficacy measures such as overall survival, progression free survival, duration of therapy, duration of response to ESK981 monotherapy in Cohort A and to the combination in Cohort B; response by combined RECIST v1.1 and irRECIST and irRECIST progression free survival (Cohort B only).

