7.1.6 Progression-Free Survival

Progression-free survival (PFS) is defined as the duration of time from start of treatment to time of progression or death, the event that occurs first.

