11.4 Data Analyses Plans

The primary analysis of efficacy will report the number of patients with an objective response and the associated proportion with the corresponding 95% exact binomial confidence interval separately in each cohort. In Cohort B, if stage 2 is initiated then the efficacy analysis methods will be adjusted for the interim check as described by Koyama and Chen [36].

Toxicity will be described by grade, attribution, and body system using counts and proportions. Toxicity will be described separately for each cohort.

Overall survival, progression free survival, duration of therapy, and duration of response will be displayed using a Kaplan-Meier figure and the associated median (if reached), one-year and two-year estimates with 95% confidence intervals using Greenwood's formula will be reported if there is censoring. If there is no censoring in the endpoint, then the standard mean (or median) and 95% confidence interval (or 5th and 95th percentiles) will be reported. Each endpoint will be reported separately by cohort.

Health-related quality of life assessment changes from baseline using EuroQoL-5D will be described using descriptive statistics.

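### Duration of response does not end at death, so in the planned Kaplan-Meier analysis a responder who dies without documented progression would by default be censored, which can only leave unchanged or lengthen the estimate

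*Combined protocol and SAP*

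**What the plan says.** Section 2.5 lists duration of response among the secondary efficacy measures for both cohorts: "overall survival, progression free survival, duration of therapy, duration of response to ESK981 monotherapy in Cohort A and to the combination in Cohort B".

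Section 7.1.5 starts the clock when the criteria for complete or partial response are first met, and runs it "until the first date that recurrent or progressive disease is objectively documented". Death is not named as an end point. Sections 2.5 and 11.1 only list the endpoint, and no other section adds death to it.

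Section 7.1.6, directly after, defines progression-free survival as "the duration of time from start of treatment to time of progression or death, the event that occurs first".

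Section 11.4 gives the analysis: "Overall survival, progression free survival, duration of therapy, and duration of response will be displayed using a Kaplan-Meier figure", with the median and the one- and two-year estimates, separately by cohort. Its only reference to censoring for these endpoints is when to use that form of summary: "with 95% confidence intervals using Greenwood's formula will be reported if there is censoring". It does not say who is censored or at what date, and it names no competing-risk method.

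Two other places bear on whether a responder can die with no progression on record. Section 7.1.4.3 recognises patients who stop treatment because their general health declines without objective progression, and says of them: "Every effort should be made to document the objective progression even after discontinuation of treatment". In Section 6.1, note 6 sets scans every 8 weeks for four assessments and every 12 weeks after that, but does not require imaging in follow-up for patients on another therapy.

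**The concern.** The two definitions treat the same death differently. For progression-free survival it is an event. For duration of response it is not, and Kaplan-Meier with progression as the only event has no other place for that patient than among the censored. The curve then treats the response as one that could have continued. Patients who decline and die before a scan are unlikely to have the same outlook as responders still being followed, so the censoring would probably be informative.

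At stake is how long responses are reported to last, in a trial with few responders. A few deaths handled this way can shift the median and the one- and two-year estimates, and any shift is in the favourable direction.

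**Working it through.** **Plan's own figure.** The documents state no median, event count or precision for duration of response, so there is nothing to reproduce on this endpoint. For context, the Cohort B design in Section 11.1 (stop at 4 or fewer responses in 17; success at 14 or more in 36) was recomputed as the sum over x = 5 to 17 of P(X1 = x) × P(X2 ≥ 14 - x), with X1 ~ Bin(17, p) and X2 ~ Bin(19, p). Power at 45% is 0.800, type I error at 25% is 0.0437, and the probability of early termination at 25% is 0.574. These agree with the stated 80%, 5% and 0.57. None of them depends on how duration of response is defined.

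**Number of responders.** In Cohort B, 0.45 × 36 = 16.2 are expected at the response rate of interest and 0.25 × 36 = 9 at the null rate. The success threshold of 14 is a decision limit, not an expectation.

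**Direction.** Turning an event into a censored observation removes one downward step from the Kaplan-Meier curve, and later steps are proportional to what remains. The curve can stay where it is or rise; it cannot fall. The comparator is time from response to progression or death.

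**Size under constant hazards.** Let λ be the total hazard of a response ending and d the share of endings that are deaths without documented progression.

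- Deaths counted: S(t) = exp(-λt), median m = ln 2/λ.
- Deaths censored: S(t) = exp(-(1-d)λt), median = ln 2/((1-d)λ) = m/(1-d).

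Both d and m are assumptions; the documents give neither. With m = 12 months:

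| d | Multiplier of median | Median (months) | 1-year | 2-year |
|---|---|---|---|---|
| 0 | 1.00 | 12.0 | 50.0% | 25.0% |
| 0.05 | 1.05 | 12.6 | 51.8% | 26.8% |
| 0.10 | 1.11 | 13.3 | 53.6% | 28.7% |
| 0.20 | 1.25 | 15.0 | 57.4% | 33.0% |

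At d = 0.20, medians of 9 and 14 months would become 9/0.8 = 11.25 and 14/0.8 = 17.5 months.

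**Small-sample illustration.** Take 14 invented responders with times 2, 4, 5, 6, 7, 8, 9, 10, 11, 13, 15, 18, 21 and 24 months, the last two censored. Suppose the endings at 4, then also 7, then also 9 months are deaths without documented progression.

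| Deaths censored | Median (months) | 1-year |
|---|---|---|
| 0 | 9 | 35.7% |
| 1 | 10 | 38.7% |
| 2 | 11 | 43.0% |
| 3 | 11 | 49.1% |

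The median need not move with each death: it is the same for two and three. The one-year estimate rises each time in this example.

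**The case against.** The strongest reply has four parts.

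- **Censoring is nowhere stated.** A reader might infer that the plan prescribes censoring at death. It does not; Section 11.4 is silent on who is censored. This stands, so the point is about the default that the written definition leads to. An analyst following 7.1.5 and 11.4 as they are written has no other option.
- **The route is narrow.** Note 6 in Section 6.1 continues scans until withdrawal of consent, death or two years from the first dose, whichever is later, so imaging is not tied to being on treatment. Section 7.1.4.3 asks for continued effort to document progression. For patients on another therapy, routine scans are still captured if available. This also stands and argues for a small d. It does not make d zero: a patient can decline and die between scans, and imaging on another therapy is not required.
- **Two endpoints may have two definitions.** A reader might call the difference from progression-free survival a contradiction. It is not: the endpoints have different start points and populations, time to documented progression can be defined, and deaths do count in progression-free and overall survival. What remains is that Kaplan-Meier with deaths censored does not estimate how long patients remain alive and in response. Read as time to progression alone, it needs death to be uninformative about progression, which is implausible here.
- **Noise exceeds the bias.** With 14 observed events and constant hazards, an approximate 95% interval for the median spans factors exp(±1.96/√14), about 0.59 to 1.69. Shifts of 5% to 25% lie well inside it. That is true, but the noise has no preferred direction and this shift does, and removing it needs no further patients.

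**Conclusion.** The point holds as a modest one. Because 7.1.5 leaves death out and 11.4 uses Kaplan-Meier without a competing-risk method, deaths without documented progression would by default be censored, and relative to time to progression or death the estimated duration can only stay the same or lengthen.

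The size cannot be determined from the documents. Under constant hazards the median rises by 5%, 11% and 25% for assumed d of 0.05, 0.10 and 0.20, and by nothing if no responder dies this way. A reader might conclude that the reported duration will be overstated. The documents support only that it can be.

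Nor does the point reach the trial's main conclusion. Duration of response is secondary and descriptive, with no hypothesis test or power attached. The primary response rate, the sample size and the decision rules do not change.

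**What to change.** In Section 7.1.5, end duration of response at the first of documented recurrence, documented progression, or death from any cause, so that death is treated as it is in 7.1.6.

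In Section 11.4, add that only responders who are alive without documented progression are censored, at their last adequate tumour assessment. The words "alive" and "only" matter: without them the sentence could be read as permission to censor deaths.

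The cost is one phrase in 7.1.5 and one sentence in 11.4, preferably settled before the deaths are known. No new data are needed: Section 5.5 follows patients for up to 24 months after treatment or until death, and Section 6.1 collects survival status. The downside is that the reported duration may be slightly shorter.
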